### 7.2.2 Expected Benefits

1. Participants may learn about others who have similar problems as they do, helping them feel less alone
2. Participants may feel increased accountability in their recovery by being in group
3. Participants may have less of a need for symptom-relieving medication like benzodiazepines and opioids.
4. Participants may find that they smoke fewer cigarettes and drink less alcohol.
5. Participants can learn skills for controlling behavior and improved well-being.
6. Participants may feel less depression, anxiety, stress, and pain.
7. Participants may benefit from the support of group-based intervention.
8. Participants may feel more joy and gratitude.

### 7.3 Adverse Events and Serious Adverse Events

Following NCCIH request, a detailed Data and Safety Monitoring Plan (DSMP) was designed and a DSMB assigned. Please see appendix at the end of this document. Adverse event reporting guidelines are detailed in the DSMP and copied below.

#### Definition:

In this study we will use the FDA definition of adverse events (AEs): “any untoward medical occurrence that may present itself during treatment or administration with a pharmaceutical product [or group-based treatment intervention], and which may or may not have a causal relationship with the treatment.” Serious adverse events for this trial will be defined as any AE temporally associated with the participants’ involvement in research that meets any of the following criteria:

- Results in death;
- Is life-threatening (i.e., any suicide attempt requiring emergency department or inpatient care will be a SAE, but parasuicidal gestures or self-harm that is not life-threatening or requiring immediate medical care will be an AE, but NOT a SAE; any opioid overdose requiring Naloxone reversal will be a SAE);
- Inpatient hospitalization or prolongation of existing hospitalization (other than admissions for substance use disorder, which will be classified as an AE, but this alone is not sufficient to classify as an SAE since this may be for detoxification or as a beneficial step towards recovery);
- Results in congenital anomaly/birth defect;
- Results in a persistent or significant disability/incapacity or permanent incapacity or substantial disruption to conduct of normal life functions;

- Based upon appropriate medical judgement may jeopardize the participant's health and may require medical or surgical intervention to prevent one of the outcomes listed in this definition.

#### Classification of AE Severity:

AEs will be labeled according to severity, which is based on their impact on the participants. An AE will be termed “mild” if it does not have a major impact on the participant, “moderate” if it causes the participant some minor inconvenience, and “severe” if it causes a substantial disruption to the participant's well-being. Of note, a severe AE and a serious adverse event (SAE) are distinct terms. A participant could experience a severe AE that does not meet the above-listed definition of an SAE; alternatively, a participant could experience a moderate AE that meets the SAE definition.

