12. *Suspension* or *termination* of the research, in whole or in part, based on information that indicates that the research places participants at an increased risk of harm than previously known or recognized;
13. Suspension or disqualification of an investigator by the sponsor, or others;
14. *Scientific misconduct*; or
15. Any other problem that indicates that the research places participants or others at an increased risk of harm or otherwise adversely affect the rights, welfare or safety of participants or others.

Procedures for collecting and reporting unanticipated problems:

All unanticipated problems (including AEs) will be collected by the PI or other study staff on an AE Tracking Log form, at the following time points: at study assessment time points at baseline and weeks 8, 16, 24, in each weekly survey, and additionally on an ad-hoc basis.

Reports of *unanticipated problems involving risks to participants or others* will be submitted to the IRB, DSMB and NCCIH within 5 working days of the date the investigator first becomes aware of the problem.

Reporting Unanticipated Problems that are Adverse Events:

Any unanticipated untoward or unfavorable medical occurrence, including abnormal sign, symptom, or disease, that indicates that the research places participants at increased risk of physical or psychological harm than previously known or recognized will be submitted as an AE to the IRB, DSMB, and NCCIH. The PI will provide the following information in the report:

1. a detailed description of the adverse event;

2. the basis for determining that the event is unexpected in nature, severity, or frequency;
3. the basis for determining that the event is related or possibly related to the research procedures;
4. the basis for determining that the research places participants at an increased risk of harm (i.e., a serious adverse event); and
5. whether any changes to the research or other corrective actions are warranted.

Reporting Unanticipated Problems that are not Adverse Events:

All other unanticipated problems incidents, experiences, information, outcomes, or other problems that indicate that the research places participants at an increased risk of physical, psychological, economic, legal, or social harm than was previously known or recognized will be submitted as an “Other Event” to the IRB, DSMB, and NCCIH within 5 business days. The investigator will provide the following information in the report:

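### The mild and moderate adverse event grades in Section 7.3 overlap and are not clearly ordered, and no grader is named

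*Combined protocol and SAP*

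**What the plan says.** Under the heading Classification of AE Severity, Section 7.3 states the basis of grading: "AEs will be labeled according to severity, which is based on their impact on the participants". An event is mild "if it does not have a major impact on the participant, “moderate” if it causes the participant some minor inconvenience". It is severe "if it causes a substantial disruption to the participant's well-being". The same paragraph adds that "a severe AE and a serious adverse event (SAE) are distinct terms" and notes that a moderate event may meet the serious definition. The supplied text contains no other severity scale, no rule for an event that fits two grades, and no worked example.

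The paragraph does not say who assigns the grade. On collection, Section 7.4 says: "All unanticipated problems (including AEs) will be collected by the PI or other study staff on an AE Tracking Log form". The opening of Section 7 has all events reviewed weekly by the Senior Research Coordinator and the Clinical Director, and monthly by the principal investigator. Section 6.2.3 and its Table 2 list research coordinators and clinical and medical directors as not blinded. They state that the principal investigator is blinded to arm when reviewing adverse events.

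Severity appears once more, in Section 7.4, among the contents of a report on an unanticipated adverse event: "the basis for determining that the event is unexpected in nature, severity, or frequency".

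**The concern.** A severity scale is useful only if each event has one grade and a worse event never receives a lower one. Here mild is defined by the absence of something large and moderate by the presence of something small. Those two conditions are compatible, so the boundary between them does not separate events.

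What is at stake is the safety record. Under Section 10.3.5 the DSMB receives adverse event information every six months, and an Annual Report lists and summarises events and comments on whether rates match pre-study assumptions. The stopping criteria in Section 9.4 carry no numerical thresholds, so the board works by judgement from such summaries. Two of the expected intervention risks in Section 7.2.1, practice-related anxiety and discomfort from gentle movement, could often fall in the range where the scale fails. If two staff members grade the same event differently, a mild/moderate breakdown says as much about the grader as about the event.

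**Working it through.** No arithmetic applies and the plan states no figure to reproduce. The check sets the three definitions against four levels of impact and then traces who handles the grade and where it is used.

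**The definitions.** Inputs: the three definitions in Section 7.3. Assumption: a substantial disruption and a major impact are roughly the same thing. Moderate is read literally, with a minor inconvenience as the level of the event and not as a floor.

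| Impact of the event | Mild (no major impact) | Moderate (minor inconvenience) | Severe (substantial disruption) |
|---|---|---|---|
| No inconvenience | meets | does not meet | does not meet |
| Minor inconvenience only | meets | meets | does not meet |
| More than minor, short of major | meets | does not meet | does not meet |
| Major | does not meet | does not meet | meets |

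- Row 2 shows the overlap: whatever meets the moderate wording also meets the mild wording, so moderate lies inside mild.
- Row 3 shows the inversion: an event worse than row 2 qualifies only for mild, while the lesser event may be called moderate.
- Row 4 is clean: severe is separable from the other two.

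**Where the grade is used.**

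- Serious adverse events: the criteria in Section 7.3 (death, threat to life, hospitalisation and so on) do not refer to the severity grade. Section 7.4 sends any serious event to the IRB and DSMB regardless of grade.
- Unexpectedness: severity is one of three possible grounds in the Section 7.4 report, beside nature and frequency. Nothing there links the word to the three labels in Section 7.3. The first reporting item in Section 7.4 also requires that the event be at least possibly related and indicate new or increased risk.
- Planned analyses: Section 9 contains no analysis of adverse events by severity grade.
- DSMB reports: Section 10.3.5 calls for aggregate tables plus a closed report by masked group. Its listed contents do not mention severity grade.

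**Who could grade.** Three roles are named for review. Two of them (Senior Research Coordinator and Clinical Director, weekly) are unblinded roles. One (the principal investigator, monthly) is stated to be blinded. None is named as the grader.

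**The case against.** The strongest reply is that mild, moderate and severe are ordinal labels, and that anyone grading would give the highest grade whose definition is met. That rule makes a minor-inconvenience event moderate and removes the overlap in row 2. It does not by itself repair row 3. For that, the moderate definition must also be read as a floor (at least a minor inconvenience). With both conventions the scale is exclusive and ordered, with mild reserved for events causing no inconvenience. Neither convention is written down, so the reply shows how the text might be rescued, not that it is sound. The same paragraph's remark that a moderate event may be serious sits awkwardly with moderate as a minor inconvenience, which suggests the wording missed its intent.

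A second reply is that the severity grading sheet may carry its own anchors. The tracking log form and the full monitoring plan are not in the supplied text, so this cannot be excluded. Section 7.3 does say that the reporting guidelines are copied from that plan.

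A reader might infer three stronger things, and the documents support none of them.

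- *That severity grading as a whole is arbitrary.* The severe grade stands apart, and the handling of serious events does not depend on the scale.
- *That the grades are assigned by staff who mostly know the arm and so drift by arm.* No grader is named. The principal investigator is stated to be blinded for adverse event review and, under Section 7.5, is notified of all events within 48 hours. That safeguard is partial, since Section 7.2.1 allows the same investigator to evaluate a participant with practice-related anxiety, which would tend to reveal the arm. Drift is possible; nothing shows it.
- *That the overlap changes what reaches the IRB, DSMB and NCCIH.* In Section 7.2.1, expectedness turns on the type of event, the participant's history and threat to life, not on mild against moderate. Any effect through the unexpected-in-severity judgement is limited at most.

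**Conclusion.** The point holds for the mild/moderate boundary. As written, the two grades are not mutually exclusive and not clearly ordered. This is a stated rule that does not work, not a detail left out. It affects the mild and moderate labels in the event log and in any summary that uses them.

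Its size cannot be given in numbers, because the documents report no event counts or rates. To say that every minor-inconvenience event has two valid grades only restates the overlap. No efficacy result, sample size or planned analysis depends on it.

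The conclusion rests on the ordinary meaning of the words, on substantial being close to major, and on there being no tie-break in material outside the supplied text. The unnamed grader is a second, smaller gap: it leaves open whether an either-way grade is settled by someone who knows the arm.

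**What to change.** Replace the three definitions in Section 7.3, and on the adverse event form, with exclusive and ordered grades. For example:

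- Mild: no or minor inconvenience, without interference with usual activities.
- Moderate: some interference with usual activities.
- Severe: substantial disruption of well-being or usual activities.

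State in Section 7.3 who assigns the grade. Have it assigned or confirmed without reference to arm at the principal investigator's blinded adverse event review, which is already planned. Regrade the mild and moderate events already logged in the same way.

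The cost is one paragraph, one form and a small amount of regrading. Nothing changes in the design, the sample size, the efficacy analysis or the handling of serious events.

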#### AE Attribution Scale:

AEs will be categorized according to the likelihood that they are related to the study intervention. Specifically, they will be labeled unrelated, possibly related, or definitely related to the study intervention.

### 7.4 Reporting Procedures

This study will comply with the reporting requirements from the Cambridge Health Alliance IRB. The PI will report to the CHA IRB, DSMB, and NCCIH any of the following *unanticipated problems* and *adverse events* that occur 1) during the conduct of the study, 2) after study completion, or 3) after participant withdrawal or completion:

1. *Internal adverse events* that are *unexpected*, and related or *possibly related to the research* and that indicate there are new or increased risks to participants;
2. *External adverse events* that are *serious*, *unexpected*, and related or *possibly related to the research* and that indicate there are new or increased risks to participants that require some action (e.g., modification of the protocol, consent process, or informing participants);
3. *Deviation* from the approved research protocol or plan without IRB approval in order to eliminate apparent immediate hazard to participants or harm to others;
4. *Deviation* from the approved research protocol or plan that placed participants or others at an increased risk of harm regardless of whether there was actual harm to participants or others;
5. Any event that requires prompt reporting according to the research protocol or investigational plan or the sponsor;

6. Breach of confidentiality or violation of HIPAA
7. Procedural error regardless of whether participants experienced any harm;
8. Interim analysis, safety monitoring report, publication in a peer-reviewed journal, or other finding that indicates that there are new or increased risks to participants or others or that participants are less likely to receive any direct benefits from the research;
9. Complaint by/on behalf of a research participant that indicates that the rights, welfare, or safety of the participant have been adversely affected or that cannot be resolved by the investigator;
10. Incarceration of a research participant during participation in this study (which is not currently approved for involvement of *prisoners* as participants);
11. *Noncompliance* with applicable regulations or requirements or determinations of the IRB identified by the research team or others that indicates that the rights, welfare, or safety of participants have been adversely affected;
12. *Suspension* or *termination* of the research, in whole or in part, based on information that indicates that the research places participants at an increased risk of harm than previously known or recognized;
13. Suspension or disqualification of an investigator by the sponsor, or others;
14. *Scientific misconduct*; or
15. Any other problem that indicates that the research places participants or others at an increased risk of harm or otherwise adversely affect the rights, welfare or safety of participants or others.

Procedures for collecting and reporting unanticipated problems:

All unanticipated problems (including AEs) will be collected by the PI or other study staff on an AE Tracking Log form, at the following time points: at study assessment time points at baseline and weeks 8, 16, 24, in each weekly survey, and additionally on an ad-hoc basis.

Reports of *unanticipated problems involving risks to participants or others* will be submitted to the IRB, DSMB and NCCIH within 5 working days of the date the investigator first becomes aware of the problem.

Reporting Unanticipated Problems that are Adverse Events:

Any unanticipated untoward or unfavorable medical occurrence, including abnormal sign, symptom, or disease, that indicates that the research places participants at increased risk of physical or psychological harm than previously known or recognized will be submitted as an AE to the IRB, DSMB, and NCCIH. The PI will provide the following information in the report:

1. a detailed description of the adverse event;

2. the basis for determining that the event is unexpected in nature, severity, or frequency;
3. the basis for determining that the event is related or possibly related to the research procedures;
4. the basis for determining that the research places participants at an increased risk of harm (i.e., a serious adverse event); and
5. whether any changes to the research or other corrective actions are warranted.

Reporting Unanticipated Problems that are not Adverse Events:

All other unanticipated problems incidents, experiences, information, outcomes, or other problems that indicate that the research places participants at an increased risk of physical, psychological, economic, legal, or social harm than was previously known or recognized will be submitted as an “Other Event” to the IRB, DSMB, and NCCIH within 5 business days. The investigator will provide the following information in the report:

1. a detailed description of the unanticipated problem;
2. the basis for determining that the problem is unexpected;
3. the basis for determining that the problem indicates that the research places participants at an increased risk of harm; and
4. whether any changes to the research or other corrective action are warranted.

SAE Reporting:

SAEs that are unexpected, serious, and possibly related to the study intervention will be reported to the IRB, DSMB, and NCCIH in accordance with requirements. Any SAE, whether related to study intervention or not, will be reported to the IRB and the DSMB within 5 business days. The initial SAE report will be followed by submission of a completed SAE report. SAEs that are unanticipated, serious, and possibly related to the study intervention will be reported to the NCCIH within 5 business days. Anticipated or unrelated SAEs will be handled in a less urgent manner but will be reported to the IRB in accordance with their requirements. A summary of the SAEs that occurred during the previous year will be included in the annual progress report to NCCIH. In the annual AE summary, the DSMB Report will state that they have reviewed all AE and SAE reports.

## 7.5 Follow-up for Adverse Events

Communication of Adverse Events:

The PI and the study Clinical Director will be notified of all adverse events that occur within 48 hours of it being reported to the study team. The PI will then decide what appropriate actions to take in order to ensure participant safety. These include

encouraging the participant to contact their PCP or mental health provider; contacting the participant's prescriber; or contacting the participant by phone or email to obtain updates on the adverse event. If the PI determines that a member of the participants clinical team should be contacted to provide context surrounding the potentially life-threatening AE, the study team will use the emergency contact information provided in the demographics form by the participant. In some cases, the participant may have already contacted their relevant providers, and/or the participant has already improved in which case no action is necessary.

Once the necessary steps to ensure participant safety have been enacted, the CMC medical director and/or PI will discuss what actions need to be taken with regard to the study: discontinuing the participant from the intervention temporarily until conditions have improved; discontinuing from the intervention permanently but keeping them in the study; or having them drop out of the study entirely.

## 7.6 Safety Monitoring

The PI and data analyst will review with the research coordinators data collection, data completeness and accuracy, as well as protocol compliance on a monthly basis. Study progress and safety will be reviewed monthly (and more frequently if needed). Progress reports, including participant recruitment, retention/attrition, and AEs, will be provided to the DSMB every 6 months (see DSMP for details).

### Possible Risk of Suicide:

During screening, study applicants will undergo a battery of psychological tests, including the CAT-MH, to determine their eligibility and safety of their participation in this study. Special attention will be placed on history of homicide or suicide attempts and the presence of any current imminent plan. Applicants who are actively suicidal will not receive the study interventions and will be evaluated by the PI to determine whether study participation is appropriate.

If imminent risk of suicide or danger to self or others is evidenced during a screening evaluation, then the participant will be excluded from participation and will be referred to the appropriate level of care as soon as possible. While maintaining contact with the participant, the study team member will contact the National Suicide Prevention Lifeline [contact]) via the CHA HIPAA compliant Google meet application. The PI will be responsible for overseeing risk assessment during screening and study visits. Study PI, [name], will be contacted by

page as soon as possible to help with clinical management. If the PI is unavailable, [name] (CMC Medical Director) can be consulted to cover.

If a participant describes feelings of suicidality while participating in a group, the study staff or group leader present during the group will help to manage this event with the current standard of care and will make immediate contact with the PI, [name], or clinical coverage listed above. The participant will be referred to the emergency room or the appropriate level of care, and the study staff member will contact the National Suicide Prevention Lifeline via the Google meet application. The PI will be notified within 24 hours of any suicidality.

## **8. INTERVENTION DISCONTINUATION**

### Participant Withdrawal/Termination Criteria:

#### *Withdrawal/Termination criteria for Participants:*

Participants may be discontinued from just the study intervention (“Group Discontinuation”) OR both the study intervention and study assessments (“Study Withdrawal”) at any time.

Specific reasons for discontinuing a participant (“Group Discontinuation”) from the group are:

1. Voluntary discontinuation by the participant who is at any time free to discontinue his or her participation in the group, without prejudice to further treatment.
2. Safety reasons as judged by the investigator.
3. Substance use disorder or psychiatric symptoms worsen to a level that requires a higher level of care.
4. Revealing private information about other participants in the groups.

Specific reasons for withdrawing a participant (“Study Withdrawal”) from the entire study are:

1. Voluntary discontinuation by the participant who is at any time free to discontinue his or her participation in the study, without prejudice to further treatment.
2. Safety reasons as judged by the investigator.
3. Incorrect enrollment (i.e., the participant does not meet the required inclusion/exclusion criteria) of the participant.
4. Active severe substance use disorder or level of intoxication during study procedures that precludes ability to conduct assessments.

5. Participants unable to complete baseline assessments.

Participants who discontinue will be asked about the reason(s) for their discontinuation and the presence of any adverse events. If possible, they will be seen and assessed by the Principal Investigator. Serious and Unexpected Adverse events will be followed up.

If participants are terminated from group intervention for any reason (except incorrect enrollment or safety concerns that endanger the study team), then they will still be expected to complete their outcome assessments, unless the participant revokes informed consent and withdraws from study.

Safety precautions for discontinuing a participant will be followed. Participants will be informed about discontinuation from group by the clinician leading the group and alternative treatment options will be discussed with the participant. If the participant is not available to receive this communication, then a letter will be sent informing the participant about the group discontinuation and providing alternative treatment options. Decisions about group intervention discontinuation will be made by the PI and group leaders but will be discussed with the CMC Medical Director for consultation prior to providing a group discontinuation letter.

If a participant is withdrawn from the study, they will be contacted by the Principal Investigator and informed the reason they are being withdrawn. A Withdrawal Letter will be sent informing the participant about the study withdrawal. If the participant was still in a study group, then the group discontinuation process will also be completed as described above with attention to providing alternative treatment options.

Participation in this research study is voluntary. Participants can choose not to participate, and their decision will in no way affect the quality of care they receive at their site or their working relationship with their site. Participants may elect at any point to discontinue their participation in this study.

Participants who become pregnant during the study will not be discontinued. The current standard of care for women with opioid use disorder is to be maintained on medication-assisted treatment with methadone or buprenorphine during the pregnancy. In fact, buprenorphine treatment leads to shorter duration of neonatal abstinence syndrome than methadone, leading buprenorphine to be the gold standard for treatment during pregnancy. To reduce risk of fetal exposure to naloxone, the current standard is for pregnant participants to be maintained on

buprenorphine alone (Subutex) instead of buprenorphine/naloxone (Suboxone) combination; however, the American College of Obstetricians and Gynecologists reported in their clinical guidelines that it is possible that the combination medication (Buprenorphine/Naloxone) will increasingly be prescribed as multiple recent studies have supported its safety. Importantly, in this study, we will not be prescribing buprenorphine to study participants, but rather enrolling pregnant participants taking buprenorphine prescribed by their health care provider as study participants into groups. If a participant becomes pregnant during the study, then the study team will alert the prescriber about the pregnancy and encourage the provider to follow their standard of care. Mindfulness groups during pregnancy have been shown in meta-analysis to reliably reduce anxiety, depression, and stress. Preliminary studies suggest mindfulness groups are safe and acceptable for pregnant women with opioid use disorder.

